Research Design/Plan: We propose a randomized, double-blind, trial of TMS to the left dorsolateral prefrontal cortex (DLPFC) for patients with MDD all of whom at the patient's treatment clinic are concurrently receiving pharmaceutical and psychotherapeutic interventions. Subjects will undergo TMS treatments for at least 4 weeks, but the duration of their TMS treatments may be extended (e.g. up to 8 weeks of treatment) if approved by the subject's third-party insurance plan. Arm 1 delivers active rTMS to the left DLPFC using the standard aiming strategy. Arm 2 delivers active rTMS to the left anterior DLPFC using connectivity-based, image-guided aiming. Arm 3 delivers active rTMS to the left posterior DLPFC using connectivity-based, image-guided aiming. In all three arms, rTMS is administered in an image-guided, robotically-positioned TMS (iTMS) manner to ensure therapist blinding and equivalent subject experiences across arms. In all three arms, the following stimulation protocol will be used: 10 Hz iTMS delivered in 4 sec trains with 26 sec inter-train intervals, 37.5 minutes/session (i.e. 3,000 pulses/session), 5 sessions/week, for at least 4 weeks. Neuroimaging will be used both for treatment planning and to characterize any TMS-induced network plasticity using resting-state functional magnetic resonance imaging (rs-fMRI) at week 4 of each treatment arm. Clinical assessments will be administered weekly throughout treatment at the subject's treatment clinic. Additional psychological tests will be performed at UT Health—San Antonio's Research Imaging Institute (RII) at the baseline and post-treatment visits in order to track subject progress.

Clinical Relevance: This will be the first study to determine the clinical effects of connectivity-guided iTMS in the treatment of MDD, to provide clues about the ideal neural networks (anterior DLPFC vs. posterior DLPFC) to target for more robust clinical outcomes, and to identify potential biomarkers of treatment response including changes in brain networks connectivity.

Item 3 Background	

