
Item 4 Purpose and rationale Insert purpose, objectives and research questions/hypotheses here. If you cut and paste from another document, make sure the excerpted material answers the question
	
We propose a randomized, double-blind, trial of iTMS to the left DLPFC for patients with MDD receiving treatment at the treatment clinic. In addition to treatment as usual, subjects will be randomized to receive iTMS in one of three treatment arms: Arm 1 delivers active iTMS to the left DLPFC using the SOC aiming strategy. Arm 2 delivers active iTMS to the left anterior DLPFC using connectivity-based, image-guided aiming. Arm 3 delivers active iTMS to the left posterior DLPFC using connectivity-based, image-guided aiming. In all three arms, repetitive TMS (rTMS) is administered in an image-guided, robotic manner to ensure therapist blinding and equivalent subject experiences across arms. In all three arms, the following stimulation protocol will be used: 10 Hz iTMS delivered in 4 sec trains with 26 sec inter-train intervals, 37.5 minutes/session (i.e. 3,000 pulses/session), 5 sessions/week, for at least 4 weeks. Neuroimaging will be used both for treatment planning and to characterize any TMS-induced network plasticity using resting-state fMRIs (rs-fMRIs) at week 4 of each treatment arm. Clinical assessments will be administered weekly throughout the TMS Treatment Phase. rs-fMRIs will be used both for treatment planning (baseline imaging), which guides the individualized positioning of the TMS coil, and to characterize iTMS-induced network connectivity (week 4). Clinical assessments using relevant clinician rated and self-report scales will be done weekly at the subject's treatment clinic. Other psychological tests will be performed at baseline, and week 4 when participants go to the RII for neuroimaging. Also, 1 and 3-month post-treatment clinical follow-ups will be conducted either in-person or over the phone to evaluate maintenance of clinical outcomes. If a subject's third-party insurance provider approves TMS treatment for more than 4 weeks, clinical assessments should continue on a weekly schedule and the 1 and 3-month post-treatment clinical follow-ups will be conducted (at their respective intervals) following that subject's last TMS treatment session.
 
Aim 1. In persons with drug-resistant MDD compare the treatment efficacy of connectivity-image-guided rTMS targeting anterior DLPFC (Arm 1), posterior (Arm 2) DLPFC and the FDA-approved SOC rTMS targeting protocol (Arm 3). In all 3 arms, at least 4 weeks (5 days/week) of the FDA-approved SOC stimulation protocol (10 Hz x 37.5 minutes) will be used.
 
 • Hypothesis 1a. Connectivity-based iTMS to the anterior left DLPFC will be superior to connectivity-based rTMS to the posterior left DLPFC and standard of care iTMS to the left DLPFC in relieving MDD symptoms. • Hypothesis 1b. Connectivity-based rTMS to the posterior left DLPFC will be superior to the standard of care iTMS to the left DLPFC in relieving MDD symptoms. 
Aim 2. Test for rTMS-induced changes in network functionality (plasticity) using rs-fMRI.
 
 • Hypothesis 2a. Intrinsic connectivity will be attenuated by active iTMS in networks connected to the respective treatment sites, as tested by correlation with the number of sessions received at the time of scanning and by pre-treatment-to-post-treatment contrast. • Hypothesis 2b. Treatment-induced decreases in connectivity will correlate with symptom improvement within and across treatment arms.

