Step-by-Step Methods: We propose to study 150 subjects (i.e. 50 per arm) who meet criteria for 1) MDD as determined by the MINI and 2) treatment resistance as determined by the MADRS) and the outlined study inclusion criteria. We anticipate recruiting and screening approximately 300 male and female subjects, in order to meet the target enrollment goals. To account for subject dropouts and retain a sample of 150 subjects completing the double-blind treatment phase (50 per treatment group), 198 eligible subjects (66 in each group) meeting MDD criteria, as determined by the MADRS, and the study inclusion criteria outlined above, will be randomized for the study. Subjects will be recruited at their treatment clinic from the institution's MDD out-patient program by the Site-Principal Investigator's team. Subjects will be screened for pregnancy and for metal objects in the body before enrolling in the study. The RII Principal Investigator's (PI) team will randomly assign subjects to one of the three treatment arms as part of the generation of neuroimaging-based treatment plans. In addition to rTMS treatments, all subjects will also complete treatment as usual at their treatment clinic, including regular medication management encounters with their attending psychiatrist and therapy sessions as part of their MDD treatment. An effort will be made to limit the disruptions in subjects' treatment by working research assessments and rTMS around their expected programming. Once enrolled, all subjects (N=198, 66 per treatment arm, expecting to retain 50 completers) will be imaged at the RII using a research-dedicated 3T Siemens TIM/Trio MRI scanner (Siemens, Erlangen, Germany) with an eight-channel phased array coil. Structural imaging will be obtained only once, upon enrollment. Structural images will be used for rTMS treatment planning (described below) and for spatial normalization to a standard anatomical template. Functional images will be obtained two times (i.e. pre-treatment and post-treatment-week 4) across the course of the study and used to detect symptom-specific network abnormalities and treatment-induced plasticity. Each subject will wear foam earplugs during each image acquisition session and each rTMS treatment session to protect subjects from the high decibel level produced by the MRI gradient and rTMS coil. See also Table of Study Procedures below.

Recruitment

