Clinical Outcomes Data Analysis plan. All pre-treatment and post-treatment MRIs will be acquired and analyzed at the RII, however, all of the statistical analysis of the symptom scores for this project will be done upon completion of recruitment and termination group blinding. The primary efficacy outcome measure will be the PHQ-9 for MDD symptoms assessed pre-treatment, weekly during treatment, post-treatment, and 1/3-months following the completion of treatment and the MADRS for the diagnosis of MDD assessed pre-treatment, post-treatment, and 1/3-months following the completion of treatment. The primary analysis will use

mixed effects regression models. Secondary analysis will focus on changes in MDD symptoms clusters, effects of the intervention in mood symptoms, functioning and cognitive outcomes. Types and rates of adverse events will be summarized and compared across the study groups. The durability of benefit and the clinical significance of PHQ-9 changes will be explored. Non-compliance to protocol as defined as missing three consecutive irTMS sessions or receiving less than 10 irTMS sessions during treatment at their treatment clinic will be assessed for and evaluated in data analysis.

Discontinuation of Subjects. Subjects may be discontinued from study treatment and assessments at any time. Specific reasons for discontinuing a subject from this study are: 1) Voluntary discontinuation by the subject, who is at any time free to discontinue his/her participation in the study without prejudice to further treatment; 2) Clinical deterioration: The following are objective criteria for clinical deterioration, a 25% increase in the PHQ-9 at any time during the study and/or the onset of active suicidality as assessed by the study clinicians requiring treatment outside of the study protocol; 3) Evidence of intolerable adverse reaction, or unable to tolerate irTMS or MRI; 4) Non-compliance to protocol by missing three consecutive irTMS sessions or as judged by the investigator; 5) Safety reasons as judged by the investigator.

Item 7 Risks Section:

Complete the following table to describe the risks of all **research procedures** listed in Step 2, Institutional Form (items 28-34). *Do not list risks of Routine care procedures here.*

N/A, Risks are described in the informed consent document – do not complete this table.

Research procedures

example:

- History and physical
- Questionnaire
- Laboratory tests

Add or delete rows as needed

Risks

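### The primary outcome combines PHQ-9 and MADRS over several visits with no deciding scale, visit or rule for Hypotheses 1a and 1b, and the post-treatment scores have no fixed time in extended courses

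*Combined protocol and SAP*

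**What the plan says.** **Outcome.** The Clinical Outcomes Data Analysis plan (Item 6) names a single primary efficacy measure and then lists two scales. The first is the PHQ-9, for symptoms, "assessed pre-treatment, weekly during treatment, post-treatment, and 1/3-months following the completion of treatment and the MADRS for the diagnosis of MDD". The second, the MADRS, is taken before treatment, after treatment and at 1 and 3 months. The primary analysis is described only as mixed effects regression, to be run after recruitment is complete and group blinding has ended. The same paragraph adds: "The durability of benefit and the clinical significance of PHQ-9 changes will be explored". Step-by-Step Methods gives the MADRS an entry role as well: "treatment resistance as determined by the MADRS".

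**Hypotheses.** Under Item 4, Hypothesis 1a says that anterior targeting "will be superior to connectivity-based rTMS to the posterior left DLPFC and standard of care iTMS to the left DLPFC". Hypothesis 1b says that posterior targeting is superior to standard of care.

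**Timing.** Item 2 says "the duration of their TMS treatments may be extended (e.g. up to 8 weeks of treatment) if approved by" the insurer. Item 4 says "Other psychological tests will be performed at baseline, and week 4 when participants go to the RII for neuroimaging". It also says that in longer courses weekly assessments continue and "the 1 and 3-month post-treatment clinical follow-ups will be conducted (at their respective intervals) following that" subject's last session. The Post-treatment MRI paragraph places the last treatment at the end of week 4, then sets the scan after the last treatment within a 3-day window. The Table of Study Procedures puts post-treatment PHQ-9 and MADRS at Wk 5 and follow-up at Wk 8/Wk16.

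**Discontinuation.** "Subjects may be discontinued from study treatment and assessments at any time"; a 25% rise in PHQ-9 is one listed reason.

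**The concern.** A mixed model does not itself define an endpoint. It can test a slope, an average over visits or a difference at any one visit, on either scale. Because the scores are analysed after the blind is lifted, an unstated choice could be made with the arms known, and a reader of the results could not tell which one was the planned test. The two scales need not agree, so the verdict on 1a or 1b may turn on that choice.

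A second, smaller gap concerns the label post-treatment. In an extended course it could mean a score taken during treatment or one taken after the last session, depending on which passage the site follows. Whether a course is extended depends on the insurer's approval.

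**Working it through.** **Figures in the plan.** 198 are randomised to keep 150 completers, 50 per arm: 198 − 150 = 48 non-completers, 48/198 = 24.2%. The plan gives no alpha, sidedness, power, SD or planning difference, so the 50 per arm cannot be reproduced. This is not evidence that it is wrong.

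**Count of candidate endpoints (4-week course).** PHQ-9: weeks 1 to 4, post-treatment, 1 month, 3 months = 7. MADRS: post-treatment, 1 month, 3 months = 3. Total 10 scale-visit pairs.

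**Assumptions, none stated in the plan.** 50 per arm; each contrast one-sided 2.5% in the stated direction; 1a claimed only if both of its contrasts succeed on the same outcome; correlation between scales 0.5-0.8 and between visits 0.5-0.7; single-visit comparisons instead of the full mixed model.

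**False claims of 1a or 1b when no arm differs (simulation).**

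| What may count | Chance of a false claim |
|---|---|
| One scale, one visit | about 3% (1b 2.5%, 1a about 0.5%) |
| Either scale, one visit | about 5% |
| Any of the 10 pairs | about 14-19% |

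**Power at a true 0.5 SD on both scales.** The 0.5 is an assumption. Item 3 gives an effect size of about 0.5 for earlier standard-of-care trials, not for differences between these three active arms. For one contrast on one scale:

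- standard error = √(2/50) = 0.2 SD
- expected z = 0.5/0.2 = 2.5
- power = Φ(2.5 − 1.96) = Φ(0.54) = 0.705, or 70% by t test with 147 df

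By simulation for the other rules:

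| Hypothesis and true pattern | One named scale | Either scale | Both scales |
|---|---|---|---|
| 1b, posterior 0.5 SD above standard of care | 70% | 79-84% | 56-61% |
| 1a, anterior 0.5 SD above both, posterior equal to standard of care | 56% | 66-73% | 39-45% |
| 1a, arms 0.5 SD apart in steps | 70% | 79-84% | 56-61% |

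For 1b, one scale is significant and the other is not in 18-29% of trials.

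**Timing of the post-treatment scores.** Item 4 and Step-by-Step Methods tie the second imaging visit to week 4. The table puts the scores at Wk 5. The 3-day window can carry a 4-week course into Wk 5, so these agree when treatment stops at week 4. In an 8-week course Wk 5 is on treatment, whereas a score taken after the last session comes after week 8. No passage chooses between them.

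**Timing of follow-up.** Counted from the last session, an L-week course gives weeks L + 4 and L + 12. For L = 4 this is 8 and 16, as in the table. For L = 8 it is 12 and 20.

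**The case against.** The plan is less open than a bare list of scales and visits suggests. Both hypotheses concern symptom relief, the analysis plan gives symptoms to the PHQ-9 and diagnosis to the MADRS, and it discusses clinical significance for the PHQ-9 only. Calling durability exploratory points away from the 1- and 3-month visits. This stands as a leaning, but the same sentence puts both scales and the follow-up visits in the primary outcome, and the wording never picks one visit.

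The arithmetic also has limits. It uses single-visit tests, and disagreement between correlated scales is partly sampling variation that would remain after one scale is named; only its interpretation would change. If either scale counts at one visit, the false-claim rate is about 5%, which is modest. The larger exposure comes from free choice of visit.

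Two stronger readings are tempting. A reader might infer that follow-up timing is undefined in extended courses. It is not: Item 4 and the 1 Month/3 Month Follow-Up text both count from the last session, and only the table's Wk 8/Wk16 labels disagree. A reader might also quote about 12% (one scale) or 18-21% (two scales) for the false-positive rate at one visit. Those figures count any of three contrasts in either direction, whereas the stated hypotheses are directional and 1a names two contrasts together.

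Finally, no passage proposes deleting scores observed before discontinuation, so the step on discontinued subjects supports the new endpoint; it does not correct a stated error.

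**Conclusion.** The concern holds and should be fixed. The plan names two scales and ten post-baseline scale-visit pairs as primary and gives no rule for deciding 1a or 1b. If that choice stays open after unblinding, the chance of a false claim could rise from about 3% to about 14-19%, and power for 1b could lie anywhere from 56% to 84% depending on the rule adopted. These sizes rest on the assumed correlations, the one-sided 2.5% tests, 50 per arm and, for power, the 0.5 SD difference. The absence of a rule rests on the text alone.

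The timing gap is narrower: it covers the post-treatment PHQ-9 and MADRS in courses longer than 4 weeks. The documents do not support extending it to the 1- and 3-month follow-ups, where only the table's labels need correcting. Nor do they show that the sample size is wrong.

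**What to change.** Before unblinding:

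1. Name one primary endpoint. One option is the between-arm difference in change from the imaging institute's baseline PHQ-9 to the scheduled week-4 PHQ-9, in all randomised subjects, from the planned mixed model with visit as a category. Week 4 is common to all arms and precedes any extension. State which baseline applies, because the Recruitment section also lets the intake score serve, and fix the assessment day. Make the MADRS key secondary and the 1- and 3-month results secondary.
2. State that 1a requires both of its contrasts and that 1b is tested separately, each in the stated direction at one-sided 2.5%. Two claims at 2.5% cannot exceed 5% together.
3. As support, because assessments may end on account of the PHQ-9 itself, keep every PHQ-9 up to and including discontinuation in the model. Request the week-4 PHQ-9 from discontinued subjects who agree.
4. Reconcile Item 4, Step-by-Step Methods, the Post-treatment MRI paragraph, the table and the analysis plan on when post-treatment scores are taken in extended courses. Relabel the table's follow-up columns to match the text.

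The cost is wording, plus one already scheduled questionnaire for some of the 48 planned non-completers. Treatment does not change. The downsides are real: the MADRS and later visits lose primary status; the PHQ-9's two-week recall at week 4 begins before all 20 sessions are complete; and one named scale has less power than an either-scale reading (70% against 79-84% for 1b).

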One month and three months after the final irTMS treatment session, participants will be interviewed (either in-person or over the telephone) by a member of the research team. Results from these assessments will be stored on the RII's secure XNAT server..

Table of Study Procedures:

Phase	Pre-Study			TMS Treatment Phase (at the clinic & the RII)				Post-Treatment (at the RII)	1 Month/ 3 Month Follow-Up (in-person or via telephone)
	Clinic Intake	Baseline	MRI Appt	Wk 1	Wk 2	Wk 3	Wk 4	Wk 5	Wk 8/Wk16
Review Medical History	X								
Informed Consent		X							
Metal Screening		X							
Patient Health Questionnaire-9 (PHQ-9)		X		X	X	X	X	X	X
Montgomery-Ashberg Depression Rating Scale (MADRS)			X					X	X
Adverse Events Monitoring			X	X-X	X-X	X-X	X-X	X	X
Concomitant Medications/Treatment		X		X-X	X-X	X-X	X-X	X	X
Structural MRI			X						
Intrinsic Connectivity by Blood- Oxygen-Level-Dependent Functional MRI			X					X	
Motor threshold assessment			X					X	
irTMS Treatment (at least 20 weekdays)				X-X	X-X	X-X	X-X		
Participant Blind Form							X		
Independent Evaluator Blind Form							X		

Data Protection. Data will be coded using an assigned number. Data collected during treatment will be placed into locked cabinets at the subject's treatment clinic's offices. Every member of the research team will be trained and monitored about how to handle and protect both medical and research records. Furthermore, the research team strictly controls access to study data. No identified data (either copies or originals) will be maintained at the study site. The study site will maintain a list of assignment numbers for the purpose of linking subsequent research materials.

Risk/Benefit Assessment.

Risks and Side Effects related to the irTMS applied to Dorsolateral Prefrontal Cortex Brain Region:

- Likely, some may be serious. In 100 people, approximately 20-30 may have:
 - Mild headache
 - Scalp and/or Facial pain/discomfort
 - Scalp and/or Facial Muscle Twitching
 - Neck pain
- Less Likely, some may be serious. In 100 people, approximately 5-10 may have:
 - Dizziness
 - Sleepiness
- Rare and Serious. In 100 people, approximately 1-2 may have:
 - Seizures

Risks and Side Effects related to the Robot placement of the irTMS include those which are:

- Rare and Serious. In 100 people, approximately 0-1 may have:

- Physical injury from the robotic device.

Risks and Side Effects related to the MRI include those which are:

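### MADRS is not measured during treatment, so a MADRS-only mixed model is close to a completer analysis and, where withdrawal depends on the PHQ-9, understates a true arm difference

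*Combined protocol and SAP*

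**What the plan says.** The primary outcome sentence (Item 6, Clinical Outcomes Data Analysis plan) lists two scales. One is "the PHQ-9 for MDD symptoms assessed pre-treatment, weekly during treatment, post-treatment, and 1/3-months following the completion of treatment". The other, for which no weekly assessment is planned, is "the MADRS for the diagnosis of MDD assessed pre-treatment, post-treatment, and 1/3-months following the completion of treatment". The Table of Study Procedures agrees. PHQ-9 is marked at baseline, in each of weeks 1 to 4, at week 5 and at follow-up. MADRS is marked at the baseline MRI appointment, at week 5 and at follow-up, with weeks 1 to 4 empty.

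The primary model is given only as "mixed effects regression models". No covariates, covariance structure, analysis set, missing-data method or auxiliary variable is stated.

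The Discontinuation of Subjects section lets a subject be taken off both study treatment and assessments. It gives five reasons. The second, clinical deterioration, is defined by "a 25% increase in the PHQ-9 at any time during the study and/or the onset of active suicidality as assessed by the study clinicians". The Risk Minimization text also withdraws subjects whose condition worsens significantly.

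Step-by-Step Methods plans for loss: "To account for subject dropouts and retain a sample of 150 subjects completing the double-blind treatment phase", 198 are to be randomised.

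Item 4 reads differently on the schedule: "Clinical assessments using relevant clinician rated and self-report scales will be done weekly". It names no scale, and the procedures table has no weekly clinician-rated symptom scale.

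**The concern.** Naming a mixed model can suggest that dropout is dealt with, because such a model uses every score a subject gave before leaving. That works for the PHQ-9, which has weekly scores. For the MADRS, someone who leaves in weeks 1 to 4 has no on-treatment score to use. Unless a later MADRS is obtained, a MADRS-only model treats that person as if the outcome would have matched that of remaining subjects with the same baseline MADRS.

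The protocol gives a reason to doubt this for some leavers, since a rise in the on-treatment PHQ-9 is itself a ground for withdrawal. If one arm does worse, more of its deteriorating subjects may drop out of the MADRS comparison, and the arms then look more alike than they are. All three arms are active, so true differences may be modest and attenuation matters. The score that explains this part of the loss is collected, but nothing says it will be used.

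**Working it through.** **1. Planned loss.** 3 × 66 = 198 and 3 × 50 = 150, so the plan's totals are consistent. The implied loss is 16/66 = 24.2% per arm, or 48 of 198. No dropout rate is stated, so 198 cannot be reproduced from one. The 48 is a ceiling on the planned loss. It is not a count of PHQ-9 withdrawals.

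**2. What a baseline-only subject contributes.** Write Y0 for baseline MADRS and Y1 for week 5. The likelihood factors as f(Y0) × f(Y1 | Y0), with E(Y1 | Y0, arm) = α + βY0 + δ·arm. A subject without Y1 contributes only f(Y0). With a common baseline mean and unstructured covariance, δ is estimated only from subjects who have Y1, so it is the completer ANCOVA estimate.

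A numerical check used random-intercept fits to 40 simulated datasets: 66 per arm, 16 per arm baseline-only, two post-baseline visits. Assumed values were baseline mean 30 and SD 6, residual SD 8 and arm effect −4.
- Common baseline mean: deleting the baseline-only subjects moved the arm effect by 0.02 points on average (maximum 0.05). The SE was 1.36 with them and 1.38 without.
- Separate baseline means per arm: the shift averaged 0.36 (maximum 1.08), but only through the baseline means. These subjects still carry no response data.

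**3. Reach of the PHQ-9 rule.** Entry needs a PHQ-9 above 14 (Item 5), and the maximum is 9 × 3 = 27. From 21, 1.25 × 21 = 26.25, which is attainable. From 22, 1.25 × 22 = 27.5, which is not. The rule can operate only from baselines of 15 to 21.

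**4. Size of the attenuation.** The documents give no SDs, correlations or withdrawal rates, so every input below is an assumption. Differences are absolute MADRS points at the end of treatment.

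| Set | Assumptions | True (full-data) difference | MADRS only | With weekly PHQ-9 |
|---|---|---|---|---|
| A | 66 per arm, 500 trials per scenario; PHQ-9/MADRS change correlation 0.8; 25% rule plus dropout linked to week-2 non-improvement; about 23% missing in the worse arm | 3.05; 4.60; 6.20 | 2.77; 4.21; 5.71 | 3.04; 4.64; 6.21 |
| B | 150,000 per arm; MADRS correlation with latent severity 0.6 to 0.9; 25% rule removes 7–13% of the worse arm and 4–8% of the better; 0–15% further random loss | 4.68 to 4.90 | 3.95 to 4.48 | 4.67 to 4.89 |
| C | 25% rule alone or with 15% random loss; applied strictly or half the time | – | 6–10% too small | within about 0.02 of full data |

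Attenuation = 1 − estimate/true value.
- Set A: 1 − 2.77/3.05 = 9.2%; 1 − 4.21/4.60 = 8.5%; 1 − 5.71/6.20 = 7.9%.
- Set B: from 1 − 4.48/4.90 = 8.6% to 1 − 3.95/4.79 = 17.5%. MADRS-only likelihood and completer ANCOVA agreed to within 0.02.
- Over the three sets: roughly 6 to 18%.

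**5. No true difference.** Sets A and C showed no bias in the contrast. In set B every method stayed within about 0.15 of zero; the 0.15 was a PHQ-9-assisted estimate in one of twelve scenarios, where the full-data value was 0.02. The completers' control-arm mean was nevertheless about 1 to 2.6 points too low (for example 18.99 against 21.56), so improvement within an arm would be overstated.

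**The case against.** **The plan does not commit to the model criticised.** It mentions neither a MADRS-only fit nor a completer set, and a joint model is not excluded. This stands. A reader might infer that a completer analysis is planned, and the text does not support that. The gap is that nothing directs the analyst to the PHQ-9.

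**The status of the MADRS is unclear.** The sentence speaks of one primary measure and ties the MADRS to diagnosis, while the weekly PHQ-9 is much less exposed. This stands as an ambiguity, but the MADRS is in the primary outcome sentence and is the only clinician-rated severity scale scheduled.

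**Leavers may still give a MADRS.** The 1- and 3-month contacts are timed from the last treatment session and may be by telephone, and subjects with fewer than 10 sessions are to be considered in the analysis. This stands. It would be too strong to say that every early leaver has only a baseline MADRS.

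**The PHQ-9 explains only part of withdrawal.** The 25% rise is half of one of five reasons, and it cannot occur from a baseline of 22 or more. This stands. The documents do not support saying that the PHQ-9 drives withdrawal in general, or that it explains most of the missing data.

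**The simulations suit the remedy.** Set A's extra dropout mechanism is not in the documents. If the rule is applied strictly, nobody beyond the threshold has a week-5 MADRS, so imputation extrapolates and its near-perfect recovery reflects the assumed model. This largely stands, although sets B and C show attenuation without set A's mechanism.

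**The bias is small.** In set A it is 0.28 to 0.49 points, or 0.20 to 0.36 of an illustrative SE of 1.37. In set B it reaches 4.79 − 3.95 = 0.84 points, about 0.6 of that SE. It is modest but systematic, and cheap to reduce.

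**Conclusion.** The point holds in a limited form. Early leavers without a later MADRS add almost nothing to a MADRS-only mixed model; that follows from the schedule and the likelihood. Where their withdrawal depends on the PHQ-9, a true MADRS difference is attenuated by roughly 6 to 18% under assumed inputs. The size for this trial cannot be derived from the documents.

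A reader might infer a risk of false-positive findings. The calculations do not show one: the contrast was essentially unbiased when the arms did not differ. Nor can it be claimed that PHQ-9-assisted analysis cures all missing data. Losses through intolerance, suicidality or choice are repaired only as far as the PHQ-9 history predicts them.

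This should be settled in the SAP, but it does not undermine the trial. If Item 4 were meant to include a weekly MADRS, most of the problem would disappear, which is one more reason to reconcile those passages.

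**What to change.** Specify before unblinding, since the plan places the symptom analysis after blinding ends:

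- Analyse the MADRS on all randomised subjects, with baseline MADRS and all observed PHQ-9 scores, including any score that triggered withdrawal, as auxiliary information. Use multiple imputation within arm or a joint PHQ-9/MADRS repeated-measures model.
- Use any follow-up MADRS obtained after withdrawal.
- Add a sensitivity analysis for data not missing at random, such as progressively worse imputed MADRS values for leavers.
- Separately, reconcile Item 4's weekly clinician-rated scales with the procedures table and the Clinical Outcomes Data Analysis plan.

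The cost is SAP wording and modest programming, with no new visits or data. The downside is dependence on the imputation model, including some extrapolation beyond the withdrawal threshold; the sensitivity analysis should show how much this matters.
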